This will provide up to 2 nurses, 1 therapist and 1 doctor in each simulation. This will provide 4 datasets for analysis at each hospital and this process will be repeated at up to 4 hospitals to deliver up to 16 datasets. Each group will participate in a 30 minute simulation which will simulate a patient having an accidental fall and will be recorded. Observation with notes by the investigator will inform discussion in the focus group to follow. The participant will be reconsented after the simulation as they will now be made aware that the focus is specifically on patient falls rather than all aspects of patient safety. If participants wish to withdraw they will be informed that, as per the initial consent form, their data to this point will be retained and used anonymously. In preparation for the focus group Critical Decision Method will be used to extract themes and codes to inductively generate a questionnaire for a future study. If the participant agrees to continue they will then join a larger group for the discussion around the simulation. This will be recorded for the investigators use only and the subsequent analysis will be fed back to the participants prior to publication and any further study to verify an accurate summary of the discussion. Patient and Public Involvement (PPI) representatives will be consulted on the evolving themes for their insights.

Participant numbers:-									
Hospital Site	Site 1		Site 2		Site 3		Site 4		Totals
Morning	Day 1	Day 2	Day 1	Day 2	Day 1	Day 2	Day 1	Day 2	
1 st Simulation 08.30-9.00	1 x Doctor 1 x Therapist 2 x Nursing Team	1 x Doctor 1 x Therapist 2 x Nursing Team	1 x Doctor 1 x Therapist 2 x Nursing Team	1 x Doctor 1 x Therapist 2 x Nursing Team	1 x Doctor 1 x Therapist 2 x Nursing Team	1 x Doctor 1 x Therapist 2 x Nursing Team	1 x Doctor 1 x Therapist 2 x Nursing Team	1 x Doctor 1 x Therapist 2 x Nursing Team	Up to 32 participants
2 nd Simulation 9.30-10.00	1 x Doctor 1 x Therapist 2 x Nursing Team	1 x Doctor 1 x Therapist 2 x Nursing Team	1 x Doctor 1 x Therapist 2 x Nursing Team	1 x Doctor 1 x Therapist 2 x Nursing Team	1 x Doctor 1 x Therapist 2 x Nursing Team	1 x Doctor 1 x Therapist 2 x Nursing Team	1 x Doctor 1 x Therapist 2 x Nursing Team	1 x Doctor 1 x Therapist 2 x Nursing Team	Up to 32 participants
Focus Group 10.00-12.00	8 Participants from the 2 morning Simulations discuss the simulation together								Up to 8 datasets
Afternoon									

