All participants will be reconsented privately before the focus group but after the simulation to disclose the deliberate use of the words patient safety versus fall prevention and to allow them to withdraw from the study should they wish to do so. The participants will then be given a reconsent information sheet, offered the opportunity to withdraw and where happy to continue to the focus group the participant will be asked to sign a reconsent form with the exact nature of the research clarified. If participants wish to withdraw they will be informed that, as per the initial consent form, their data to this point will be retained and used anonymously. As the participant will be working as part of a team in the simulation it would not be possible to remove the discussions and actions from the recording and subsequent notes. The investigator will reassure them that because they will have only used their pseudonym in the simulation they will not be identifiable. The simulation is to stimulate discussion of a shared experience in the focus group and not any one persons actions or contributions, as such the main body of work will be derived from the focus group not the simulation.

Should there be any subsequent amendment to the final protocol, which might affect a participant's participation in the trial, continuing consent will be obtained using an amended Consent form which will be signed by the participant.

STUDY REGIMEN

1. Email invite with participant information sheet will be sent by senior team member. Posters will be displayed in clinical areas. Investigator will also attend any team meetings, where invited, to discuss the nature of the study.
2. Participant will indicate interest by contacting the investigator via email, WhatsApp, phone or QR code. The QR code leads to a quick microsoft form which gives the potential participant chance to check they meet the inclusion criteria and give the their Investigator contact email address or phone number. This form is sent to the Investigator's student Microsoft forms 365 account and it automatically emails me to let me know there is a response waiting for me.
3. Investigator will contact the prospective participant and answer any questions
4. Participant will meet the investigator in a convenient and safe location to give consent.
5. Participant will be allocated a unique study identity code number and pseudonym which will be recorded in the Trial Recruitment Log (TRL) alongside their demographic and

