- contact details. The TRL will be kept securely in a password protected file on UoN one drive.
6. Potential participants who choose not to go into the study will only be on the TRL as their unique identifier and their reason for not participating if they give one but they will not be asked. All personal identifying details will be deleted immediately. The investigator will not attempt to contact them again.
 7. Participants who are happy to continue into the study will choose 1 of 2 dates possible for the simulation and focus group.
 8. Details of location and agenda for the simulation and focus group will be sent to the participant.
 9. All participants will be contacted by phone or email via their preferred form of communication identified when recruited at step 5 to remind them the day before the simulation and focus group.
 10. Participants will arrive at the simulation lab and will be given a pseudonym, name badge and role card (the pseudonym is to use during the simulation and recording to protect their identity to other participants and on the recording). The pseudonym will also be recorded alongside their unique identifying number and demographics on the TRL. The TRL will be kept securely in a password protected file on UoN one drive in accordance with the data management plan (DMP).
 11. The investigator will observe with notes during the simulation (30 mins). This will be recorded.
 12. On completion of the simulation the investigator will re-consent the participant as they will now realise that the patient safety theme was fall prevention. (5 mins)
 13. On completion of the **re-consent process** a guided critical decision method session will detail the timeline of events and key decisions (30 mins). This will be recorded on University of Nottingham property Dictaphones and the data securely saved as per the DMP.
 14. On completion of the timeline, the semi structured focus group will begin, facilitated by the investigator. This will be recorded on University of Nottingham property Dictaphones and the data securely saved as per the DMP.
 15. The investigator will close the discussion group and explain that the participant will be contacted again in order to share the analysis and themes to verify an accurate understanding of discussion. Participant will be given the option to opt out of this stage.
 16. Investigator will transcribe and analyse themes evolving from the session using Nvivo14.

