The incident portrayed in the simulation can evoke strong emotions either from previous professional or personal experience. Should a participant become distressed the investigator will initiate the distress protocol.

It is not anticipated that the confidentiality of participants will be breached however it is likely that participants may know each other and/or are working with or have worked with each other previously. Whilst a confidentiality agreement will be discussed with each participant and a request not to share any information outside the simulation lab and focus group room there is a chance that this will happen. In this instance the participants will be asked to report this to the investigator who will approach the relevant senior team in the hospital. Depending on the nature of the issue and the available evidence the senior management team will take appropriate action. An apology will be offered where appropriate to the affected participant.

ETHICS COMMITTEE AND REGULATORY APPROVALS

The study will not be initiated before the protocol, consent forms and participant information sheets have received approval / favourable opinion from the Research Ethics Committee (REC), the respective National Health Service (NHS) or other healthcare provider's Research & Development (R&D) department, and the Health Research Authority (HRA) if required. Should a protocol amendment be made that requires REC approval, the changes in the protocol will not be instituted until the amendment and revised informed consent forms and participant information sheets have been reviewed and received approval / favourable opinion from the REC and R&D departments. A protocol amendment intended to eliminate an apparent immediate hazard to participants may be implemented immediately providing that the REC are notified as soon as possible and an approval is requested. Minor protocol amendments only for logistical or administrative changes may be implemented immediately; and the REC will be informed.

The study will be conducted in accordance with the ethical principles that have their origin in the Declaration of Helsinki, 1996; the principles of Good Clinical Practice and the UK Department of Health Policy Framework for Health and Social Care, 2017.

INFORMED CONSENT AND PARTICIPANT INFORMATION

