CRFs will be treated as confidential documents and held securely in accordance with regulations. The investigator will make a separate confidential record of the participant's name, pseudonym and Participant Study Number, to permit identification of all participants enrolled in the study, in case additional follow-up is required. This will be held within the TRL. CRFs shall be restricted to those personnel approved by the Chief or local Investigator and recorded as such in the study records.

All paper forms shall be filled in using black ballpoint pen. Errors shall be lined out but not obliterated by using correction fluid and the correction inserted, initialled and dated.

The Chief or local Investigator shall sign a declaration ensuring accuracy of data recorded in the CRF.

Source documents

Source documents shall be filed at the investigator's site and may include but are not limited to, consent forms, study records, field notes, interview transcriptions and audio records. A CRF may also completely serve as its own source data. Only the chief and local investigator and shall have access to study documentation other than the regulatory requirements listed below.

Direct access to source data / documents

The CRF and all source documents shall be always made available for review by the Chief Investigator, Sponsor's designee and inspection by relevant regulatory authorities.

DATA PROTECTION

All study staff and investigators will endeavour to protect the rights of the study's participants to privacy and informed consent, and will adhere to the Data Protection Act, 2018. The CRF will only collect the minimum required information for the purposes of the study. CRFs will be held securely in a password protected file on UoN one drive. Access to the information will be limited to the study staff and investigators and any relevant regulatory authorities (see above). Computer held data including the study database will be held securely and password protected. All data will be stored on a secure dedicated web server. Access will be restricted by user identifiers and passwords (encrypted using a one way encryption method).

Electronic data will be backed up every 24 hours to both local and remote media in encrypted format.

QUALITY ASSURANCE & AUDIT

INSURANCE AND INDEMNITY

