In compliance with the ICH/GCP guidelines, regulations and in accordance with the University of Nottingham Code of Research Conduct and Research Ethics, the Chief or local Principal Investigator will maintain all records and documents regarding the conduct of the study. These will be retained for at least 7 years or for longer if required. If the responsible investigator is no longer able to maintain the study records, a second person will be nominated to take over this responsibility.

The study documents held by the Chief Investigator (CI) on behalf of the Sponsor shall be finally archived at secure archive facilities at the University of Nottingham. This archive shall include all anonymised audio recordings, study databases and associated meta-data encryption codes.

DISCONTINUATION OF THE STUDY BY THE SPONSOR

The Sponsor reserves the right to discontinue this study at any time for failure to meet expected enrolment goals, for safety or any other administrative reasons. The Sponsor shall take advice as appropriate in making this decision.

STATEMENT OF CONFIDENTIALITY

Individual participant medical or personal information obtained as a result of this study are considered confidential and disclosure to third parties is prohibited with the exceptions noted above.

Participant confidentiality will be further ensured by utilising identification code numbers to correspond to treatment data in the computer files.

Such medical information may be given to the participant's medical team and all appropriate medical personnel responsible for the participant's welfare.

If information is disclosed during the study that could pose a risk of harm to the participant or others, the researcher will discuss this with the CI and where appropriate report accordingly.

Data generated as a result of this study will be available for inspection on request by the participating physicians, the University of Nottingham representatives, the REC, local R&D Departments and the regulatory authorities.

PUBLICATION AND DISSEMINATION POLICY

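### People withdrawing at re-consent are told a pseudonym makes them unidentifiable, but the plan keeps a log that identifies every participant and expects colleagues to know each other

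*Combined protocol and SAP*

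**What the plan says.** Participants join the simulation believing that the topic is patient safety in general. Afterwards they are told that it is falls, and are re-consented. The Informed consent section sets out what those who then wish to leave will hear. Under the terms of the initial consent form, "their data to this point will be retained and used anonymously"; the same words appear under Study Configuration. Because they acted as part of a team, "it would not be possible to remove the discussions and actions from the recording and subsequent notes". Then: "The investigator will reassure them that because they will have only used their pseudonym in the simulation they will not be identifiable".

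Four other places bear on that assurance:

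- **Study Regimen, step 10**, on why a pseudonym is issued: "the pseudonym is to use during the simulation and recording to protect their identity to other participants and on the recording".
- **Ethical and Regulatory Aspects**, on who will be in the room: "it is likely that participants may know each other and/or are working with or have worked with each other previously".
- **Records, Case Report Forms**: "The investigator will make a separate confidential record of the participant's name, pseudonym and Participant Study Number". Its stated purpose is that everyone enrolled can be identified if further follow-up is needed, and it is held in the TRL. Study Regimen steps 5 and 10 also put the pseudonym in the TRL, next to the code number, demographic details and contact details.
- **Study Configuration**, on team make-up: "This will provide up to 2 nurses, 1 therapist and 1 doctor in each simulation". Under Analyses, Methods, each person plays their own profession.

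**The concern.** The assurance gives one reason (a pseudonym was used) for one unlimited conclusion (the person cannot be identified). The plan contradicts that conclusion in two ways: it keeps a key whose purpose is identification, and it places people among colleagues who probably know them. The retained material is pseudonymised, not anonymous.

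What is at stake is the accuracy of what participants are told. Those who hear the sentence have just learned that the topic was withheld, and that their part in the recording cannot be taken out. They work at the participating Trust and were first approached through their own management, so recognition at work may matter to them.

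**Working it through.** The plan gives no statistical figure on this point. The check compares passages of the protocol and makes one count.

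**1. Assurance against log.** Informed consent says that pseudonym use means the person is not identifiable. The Case Report Forms section keeps names, pseudonyms and study numbers together so that participants can be identified. Both cannot be true of the same person while the record exists.

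**2. Is the link removed for someone who withdraws?** Study Regimen step 6 deletes identifying details at once, but only for people who choose not to enter the study. No equivalent is stated for people who enter and then withdraw. Record Retention and Archiving keeps all study records for at least 7 years. Nothing in the text available says that the link is destroyed.

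**3. Pseudonym against setting.** Step 10 says that the pseudonym protects identity from the other participants. Ethical and Regulatory Aspects says they probably know, or have worked with, one another. A badge with another name does not conceal a known colleague in a team of four.

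**4. Role within a session.** Inputs, from Study Configuration and Figure 2: 4 sites, 2 days per site, 4 simulations per day, and a team of 1 doctor, 1 therapist and 2 nursing staff.

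- Simulations: 4 × 2 × 4 = 32.
- Participants: 32 × 4 = 128, which reproduces the stated maximum.
- Alone in their role within the session: 32 × (1 doctor + 1 therapist) = 64.
- Share: 64 / 128 = 50%.
- Nursing staff: 32 × 2 = 64, each narrowed to 1 of 2.

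The count assumes full recruitment and attendance. An absent doctor or therapist lowers it; an absent nurse leaves the other nurse alone in that role.

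**The case against.** The best defence is context. The sentence before the assurance concerns the recording and notes, so the sponsor may have meant only that outsiders could not identify anyone from retained data. The sentence after it says that the main body of work comes from the focus group, and someone who leaves at re-consent contributes nothing there. Ethical and Regulatory Aspects openly acknowledges that participants may know each other, provides for a confidentiality agreement and says how a breach is handled. The TRL is password protected, and Study Regimen step 18 requires anonymity when themes are brought together.

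This limits the likely harm but does not make the sentence true. The sentence carries no restriction to outputs or outside readers. Password protection limits who can use the key; it does not remove it.

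A reader might infer more than the documents support:

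- **That the assurance persuades undecided people to stay.** The text is directed at those who already wish to leave.
- **That consent to keep the data is invalid or open to challenge.** The initial consent form sets the retention term before the simulation. Recruitment also says that consent to use a withdrawn person's data will be sought, which is not fully aligned with Informed consent. Neither supports a conclusion about validity.
- **That half the participants are identifiable by role alone.** Up to 32 doctors share one role and up to 32 therapists another, so the session must also be known.
- **That every participant will certainly be recognised.** The protocol says that acquaintance is likely, not certain.
- **That the archive stores the recordings with the pseudonym key.** The text is "This archive shall include all anonymised audio recordings, study databases and associated meta-data encryption codes". It calls the recordings anonymised, and the codes may be file-encryption keys.
- **That a rule on labelling quotations is missing.** The publication policy text was not available for this review. Dropping site labels would also have a cost in a four-hospital study of whether experience is universal.

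**Conclusion.** The point stands as a correction of wording. The assurance given to people who are withdrawing claims a property that the design does not have. The contradiction with the Case Report Forms section is direct, and so is that between step 10 and Ethical and Regulatory Aspects. Neither depends on the archive text.

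On size, the log link covers every enrolled participant. Recognition by colleagues in the room is likely. Role plus session singles out 64 of 128 at full recruitment, to anyone who knows who attended. That figure counts all participants; the number who will withdraw and hear the assurance is unknown.

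The information sheet, consent forms, re-consent sheet and data management plan were not available and may qualify the assurance. Accurate wording there would still conflict with what the protocol says the investigator will tell people. No sample size or analysis changes.

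**What to change.** 1. In Informed consent, replace the assurance with an accurate statement: names will not appear in transcripts or reports; colleagues who were present may recognise the person; the pseudonym is linked to the name in a protected log with restricted access.
2. In Informed consent and Study Configuration, describe data retained after withdrawal as pseudonymised for as long as the link exists. If the sponsor intends to destroy the link, say when.
3. In Study Regimen step 10, correct the stated purpose of the pseudonym so that it agrees with Ethical and Regulatory Aspects. It can keep real names off the recording; it cannot be relied on to hide people from colleagues in the room.
4. Make the re-consent sheet match.

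The cost is a wording change to the protocol and the re-consent sheet, with whatever approval the protocol requires for revised participant documents. Design, recruitment and analysis are unaffected, and no quotation-labelling rule is needed.
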